7.1.3 Follow-Up Phase

Patients will be followed for safety monitoring (30 + 4 days) after their final study drug infusion and will have an End of Study visit by telephone at the following times: either (1) at completion of the Extension Phase or (2) at early termination if the patient voluntarily withdraws consent. Patients who terminate the study prematurely will continue to be followed by having all Early Termination assessments performed. Patients who terminate the study prematurely who are unable to be on-site for the Early Termination visit will be contacted by telephone for safety follow-up.

If withdrawn from study drug, regardless of reason, the patient will continue study visits to the end of Treatment Period 12.

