11.2.2 Gout Flare Assessment

Gout flare will be assessed as part of AE collection with severity determined as described in [Section 12.2.2.3](#). Gout flares will be assessed at each study visit during the Treatment Phase using a validated definition of flares in patients with established gout ([Gaffo 2018](#)). In addition, in an exploratory manner, gout flares will be self-assessed weekly by the patient after randomization and in each Treatment Period using a weekly flare diary ([Poiley 2016](#)).

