12.2.1.1 Adverse Event (AE)

An AE is any untoward medical occurrence associated with the use of a drug (i.e., study drug) in humans, whether or not considered drug related. An AE can therefore be any unfavorable and unintended sign (including an abnormal laboratory finding), symptom, or disease temporally associated with the use of a drug and does not imply any judgment about causality. An AE can arise with use of any drug or medicinal product. A treatment-emergent AE (TEAE) is an AE that starts or worsens at any time after initiation of study drug on Day 0 of Treatment Period 1 until the End of Study Visit (30 days after completion of the last dose of study drug).

Patients will be considered enrolled in the study upon signing the ICF. During the Screening Phase (from time informed consent is signed to immediately before dosing) any clinically significant changes in the patient's health will be recorded in the patient's medical history and will not be considered as AEs. AEs

 Selecta Biosciences	PHASE 3 STUDY: SEL-212/301 VERSION: 6.1	EFFECTIVE DATE 15 DECEMBER 2022
--	--	--

(and thus SAEs) will be collected from the time the patient is dosed (infusion is started) until the end of the End of Study Visit.

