The study period during which AEs must be reported is from the time the patient is dosed until the 30 (\pm 1) days after the last infusion of study drug. During the Screening Phase (from time informed consent is signed up to the time of dosing) any clinically significant changes in the patient's health will be recorded in the patient's medical history and will not be considered as AEs.

Investigators are not obligated to actively seek AEs or SAEs in former study patients. However, if the Investigator learns of any SAE, including a death, at any time after a patient has been discharged from the study, and he/she considers the event reasonably related to the study drug, the Investigator should promptly notify the Sponsor.

12.2.3.2 **SAE Reporting Procedures**

On discovery, all SAEs should be immediately reported (latest within 24 hours of knowledge of the event) to PAREXEL Safety Services by:

Completing the SAE report form and faxing the documents to PAREXEL Safety Services, using the appropriate regional PAREXEL SAE fax numbers below:

NA (Billerica): [contact]

or

Completing the SAE report form and submitting it to PAREXEL Safety Services via email utilizing the address (es) below:

NA: [contact]

In the event that the site is unable to complete the SAE form to report the event within 24 hours of their knowledge of the event, the investigators may report the SAE over the telephone via the SAE answering service, and then provide the completed SAE form via fax or email. If questions arise regarding the reporting procedures or the specifics of the reporting of an event, sites may call utilizing the following numbers:

NA (Billerica): [contact]

The Investigator will complete the SAE form and provide all case information available at the time of the initial report. The investigator must include the following mandatory case information:

1. The patient identification number
2. The event description
3. The seriousness criteria
4. The Investigator's causality assessment

The reporting Investigator must send the written and signed SAE report by facsimile or email, within 24 hours of observing, notification of, or learning of the SAE to PAREXEL Safety Services as described above. Follow-up information regarding an SAE and the supporting data, including laboratory findings and discharge summaries, should be sent by facsimile or email to PAREXEL Safety Services within 24 hours of receipt of the information.

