Appendix A Schedule of Assessments, continued

Assessment	Scr. - 45 d to D0 (Pre-dose) ³	Double-Blind Treatment Phase														EOS¹	ET	
		TP1 ²		TP2 ²		TP3 ²		TP4 ²		TP5 ²		TP6 ²						
		D0	D21 ⁴	D0 ⁵	D7 ⁴	D14 ⁴	D21 ⁴	D28 ^{5,25}										
Tophus Assessment/Photography	X							X								X	X	
Gout Flare Assessment ²²	X	X	X	X	X	X	X	X	X	X	X	X	X	X	X	X	X	
Gout Flare Weekly Diary		Continuously on Weekly Basis ²⁴															X	
Joint Assessment (tenderness, swelling)		X						X								X	X	
Health Questionnaires ²³		X						X								X	X	
Collect Sample for sUA	X	Refer to Schedule of Assessments (Appendix B) for sUA Sample Collection during Treatment Phase															X	
PD/Uricase Activity Assessment		Refer to Schedule of Assessments (Appendix B) for PD/Uricase Activity Assessments during Treatment Phase															X	
Study Drug Administration		Refer to Schedule of Assessments in Appendix B for Study Drug Administration during the Treatment Phase																
Infusion Reaction Follow-up		Refer to Section 12.2.1.5																
Concomitant Medications / Procedures		Continuously														X	X	
AE Collection		Continuously														X	X	
SAE Collection		Continuously														X	X	

1. Phone call at 30 (+4) days after the last study drug infusion for assessment of concomitant medications/procedures, AEs, and SAEs.
2. Visit window at Day 21 of each Treatment Period is +2/-1 days; visit window at Day 7 and Day 14 of Treatment Period 6 is +2/-1 days; visit window at Day 28 of Treatment Period 6 is +3/-4 days.
3. Visit window is -2 days.
4. Assessments at this visit are permitted to be performed remotely (inclusive of collecting applicable lab draws and assessments per protocol visit windows).

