#### **6.2.8. Estimands for 'Gout Flare incidence during Treatment Periods 1-6'**

The main estimand for the key secondary efficacy endpoint 'gout flare incidence during TP1 to 6' is defined as follows:

- Population: Of all patients with gout refractory to conventional treatment defined by the study inclusion / exclusion criteria, the analysis population will include patients who were randomized to study treatment and who were dosed (ITT population).

This document is confidential.

- Variable: Incidence of gout flare during the whole treatment period from start of treatment until end of month 6. Gout flare incidence is defined as the total number of gout flares a patient experiences in respective time period divided by the length of observation of the patient in this time period.
- Population-level summary: Difference in the incidence of gout flares between each SEL-212 treatment group versus placebo for the whole treatment period (start of treatment until end of Treatment Period 6).
- Intercurrent events:
  - o All intercurrent events (as listed in 6.1 for the primary estimand) except deaths will be considered using the treatment policy strategy
  - o For deaths, the while-on-treatment strategy will be used

A second estimand for this key secondary endpoint will be defined similarly to the main estimand but with using the while-on-treatment strategy for all intercurrent events (as listed in 6.1 for the primary estimand).

These analyses will be repeated for each background medication subgroup: i) no NSAIDs or colchicine, ii) NSAIDs no colchicine, and iii) colchicine.

The main and second estimands will be repeated three times, once with the population changed to the mITT, and the other with the population changed to the all randomized set, and thirdly with the population changed to the PP set.

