### **10.3. Adverse Events / Adverse Drug Reactions**

All adverse events (AEs) will be coded using the most recent MedDRA Version. All AEs will be summarized by system organ class (SOC) and preferred term (PT) for each treatment group, for overall SEL-212 and in total for the whole study, but also for the double-blind treatment phase and the double-blind extension phase separately. A treatment-emergent AE (TEAE) is an AE that starts or worsens at any time after

This document is confidential.

initiation of study drug on Day 0 of Treatment Period 1 until the End of Study Visit (30 days after completion of the last dose of study drug). TEAEs will be further classified as treatment-emergent for the double-blind treatment phase (these are all AEs which start prior to the first dose in the extension phase) and as treatment-emergent for the double-blind extension phase (these are all AEs which start after the first dose in the extension phase or increase in intensity after start of study drug in the extension phase). Additional analysis will be performed on a subset of infusion reactions (this is a study drug-related AE that occurs within 1 hour after completion of study drug infusion) that fulfil the criteria of an Allergic Reaction/Hypersensitivity according to the Rheumatology Common Toxicity Criteria, version 2.0.

Following AEs are considered as AEs of special interest (AESIs): gout flares, infections, malignancies, viral infections, interstitial lung disease, stomatitis, infusion-related reactions including anaphylaxis, thrombosis (e.g., deep venous thrombosis, pulmonary embolism), and the following laboratory tests, if deemed clinically significant by the PI: hyperlipidemia, worsening of renal function tests, proteinuria, and leukopenia.

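### Required AE reporting ends 30 days after the last infusion while patients taken off study drug are followed to Treatment Period 12, so late adverse events, and possibly gout flares, can go unrecorded

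*Protocol*

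**What the plan says.** **Rules that end at about 30 days.** Protocol 12.2.3.1 sets the period of required AE reporting "from the time the patient is dosed until the 30" (±1) days after the last infusion. Section 12.2.4 follows AEs for 30 (+4) days after the last dose, or to an earlier end point. Footnote 1 to Appendices A and C describes the End of Study contact as: "Phone call at 30 (+4) days after the last study drug infusion for assessment of concomitant medications/procedures, AEs, and SAEs". Section 12.2.1.1 defines a treatment-emergent AE (TEAE) as one starting or worsening after first dosing "until the End of Study Visit (30 days after completion of the last dose of study drug"). SAP 10.3 uses the same cut-off: "initiation of study drug on Day 0 of Treatment Period 1 until the End of Study Visit (30 days after completion of the last dose".

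**Rules that run longer.** Protocol 7.1.3, 7.4.1.1 and 8.3.3.1 keep patients withdrawn from study drug in visits to the end of TP12. Section 7.1.3 times the End of Study call "either (1) at completion of the Extension Phase or (2) at early termination if the patient voluntarily withdraws consent". Section 7.1.2 has AEs monitored throughout the study, and the AE and SAE rows of Appendices A and C are marked continuous. Section 12.2.1.1 says AEs "will be collected from the time the patient is dosed (infusion is started) until the end of the End of Study Visit", so its end depends on which date that visit is given.

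**Flares.** Protocol 11.2.2 states: "Gout flare will be assessed as part of AE collection with severity determined as described in" the AE grading section. Section 10.6.1 has each flare recorded as an AE. Section 11.2.2 also provides for a flare assessment at every treatment-phase visit. Key secondary endpoints 8 and 9 use the treatment-policy strategy for every intercurrent event except death (Protocol 13.4.2; SAP 6.2.8 and 6.2.9). Incidence is the number of flares "divided by the length of observation of the patient in this time period".

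**The concern.** A site could reasonably follow either set of rules. Under 12.2.3.1 it would stop reporting AEs in a patient who is off study drug but still attends for months. Two things are at stake.

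*Safety.* The AEs of special interest (AESIs) include interstitial lung disease, malignancy and infection, all of which can appear late. In a stopped patient their reporting would not be required after the window closes.

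*Flare endpoints.* A treatment-policy estimand needs flares that occur after stopping. Neither document says whether the count for endpoints 8 and 9 comes from AE records or from the visit assessments. If it comes from AE records, flares can cease to be counted while the patient keeps adding observation time, which lowers that patient's rate.

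**Working it through.** **1. The plan's own timeline.** Protocol 7.1 gives a maximum participation of 383 days. Screening of 45 days, TP12 Day 0 at 11 × 28 = 308 days, and 30 days of follow-up give 45 + 308 + 30 = 383, as stated. For a patient who takes all twelve doses, the AE window ends at Day 308 + 30 = 338 and the extension at Day 12 × 28 = 336. The two sets of rules therefore agree for completers and part only for patients who stop.

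**2. Days outside the window.** With the last infusion in TP k, at nominal Day 28(k − 1), the window ends at Day 28(k − 1) + 30. Uncovered days in a period of length L are max(0, L − [28(k − 1) + 30]).

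| Last dose in | Window ends | TP1-3 (L = 84) | TP1-6 (L = 168) | To Day 336 |
|---|---|---|---|---|
| TP1 | Day 30 | 54 (64%) | 138 (82%) | 306 |
| TP2 | Day 58 | 26 (31%) | 110 (65%) | 278 |
| TP3 | Day 86 | 0 | 82 (49%) | 250 |
| TP4 | Day 114 | 0 | 54 (32%) | 222 |
| TP5 | Day 142 | 0 | 26 (15%) | 194 |
| TP6 | Day 170 | 0 | 0 | 166 |

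The difference in tolerance, ±1 day against +4 days, moves these figures by only a few days.

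**3. Share of an arm's follow-up uncovered.** The documents give neither the share of patients who stop nor when, so both are assumptions. Take stopping spread evenly over TP1-3. The mean gap is (138 + 110 + 82)/3 = 110 days in TP1-6 and (54 + 26 + 0)/3 = 26.7 days in TP1-3.

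| Share stopping | TP1-6 | TP1-3 |
|---|---|---|
| 20% | 0.20 × 110/168 = 13% | 0.20 × 26.7/84 = 6% |
| 50% | 0.50 × 110/168 = 33% | 0.50 × 26.7/84 = 16% |
| 55% | 0.55 × 110/168 = 36% | 0.55 × 26.7/84 = 17% |

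The 55% row is the complement of the 45% SEL-212 responder rate assumed in Protocol 13.1. Non-response has causes other than stopping, so it is not a forecast. Timing matters as much as share: with 55% stopping, the TP1-6 figure is 0.55 × 138/168 = 45% if all stop after the TP1 dose and 0.55 × 26/168 = 8.5% if all stop after the TP5 dose.

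These percentages become an understatement of the arm's flare rate only if flares are taken solely from AE records, sites apply 12.2.3.1 literally, the denominator is full observation time, and the true flare rate is constant and the same in stopped and continuing patients.

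**4. Safety data collected after the window.** The six-month chest X-ray, taken to look for interstitial lung disease, falls at about Day 168. For a last dose in TP1 to TP5 the window has closed by Day 142 at the latest. Safety laboratory tests also continue to TP12.

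**5. Direction.** The stopping rule in Protocol 7.4.1.1 requires sUA below 2.0 mg/dL one hour after the second infusion in TP1. That is hardly attainable on saline when screening sUA must be at least 7 mg/dL. Rule-based stopping should therefore fall mainly on the SEL-212 arms.

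**The case against.** The strongest reply is that the data will be collected anyway.

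- Flares have a scheduled assessment at every TP1-6 visit, stopped patients attend those visits, and both flare endpoints lie within TP1-6. Nothing says a flare found after Day 30 is discarded.
- Section 12.2.2 asks patients to report health changes through completion of the study and has all AEs entered in the CRF. Section 12.2.2.6 sets no time limit on abnormal findings in dosed patients.
- SAP 10.3 counts AEs separately from TEAEs, summarises AEs for the whole study and plans a listing of non-TEAEs. Pre-dose events are medical history, so that listing would mainly hold events after the window.

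This stands as evidence of intent, and it rules out two stronger readings. A reader might infer that flares in stopped patients are lost; the visit assessments mean this is only possible. A reader might also infer that any under-count is confined to SEL-212. Section 7.4.1.1 withdraws patients who lack an in-window Day 21 sUA and have no later result, or a later value above the limit, and that clause does not repeat the post-infusion condition. Stops for AEs or COVID-19 apply to every arm. Placebo patients can therefore be affected.

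The reply does not remove the conflict. The section that states the reporting duty ends it at 30 days, and the SAP can list only what sites record. The clause in 12.2.3.1 on later SAEs covers only related events in patients already discharged; a stopped patient still attending visits falls between the two rules.

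**Conclusion.** The concern holds as a contradiction between stated rules. For a patient stopped after the TP1 dose, the two readings of when AE reporting ends differ by 306 days (Day 30 against Day 336). The safety consequence follows from the text: late AEs and AESIs in stopped patients need not be reported under 12.2.3.1, although other sections invite their collection.

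The flare consequence is conditional on AE records being the source of the count and on sites applying the 30-day limit. It would then lower the flare rate mainly, not only, in the SEL-212 arms. The uncovered share is about 33% of TP1-6 and 16% of TP1-3 if half an arm stops evenly over TP1-3, and smaller with fewer or later stops. The primary endpoint is unaffected. This should be corrected, because events that were never recorded cannot be recovered at analysis.

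**What to change.** 1. Reconcile Protocol 12.2.1.1, 12.2.3.1, 12.2.4, Appendices A and C (AE rows and footnote 1) and SAP 10.3, with the schedules repeated in the SAP. AEs, SAEs, AESIs and flares should be recorded from first dose to the patient's last study visit, and for at least 30 days after the last infusion, whether or not study drug was stopped. Use one tolerance for the 30-day contact.
2. Keep the 30-day TEAE flag for on-treatment tables. State that the whole-study AE summaries by arm include events after that window.
3. In SAP 9.3.2.8 and 9.3.2.9, name the source of the flare count: visit assessment, AE record, or both with duplicates removed. Require numerator and observation time to cover the same period, to TP6 Day 28 or TP3 Day 28.

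The visits already take place, so the cost is protocol and SAP wording and a little extra CRF entry.

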8.3 Patient Completion and Withdrawal Criteria

8.3.1 Screen Failures and Replaced Subjects

A patient is considered enrolled in the study at the time of ICF signature. Any patient that is screened but not dosed will be considered a screen failure and the reason for failure will be documented.

Any patient that is randomized but not dosed will be replaced and not included in the ITT population, and the reason for not being dosed will be documented.

Within the 45-day screening window, out-of-range laboratory tests may be repeated up to 2 times before declaring a screen failure (except for COVID-19 testing as described in [Section 12.1.8.7](#)). After the 45-day screening window, patients can be re-screened once.

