10.6 Premedication

10.6.1 Gout Flares (Prophylaxis and Treatment)

All patients that are expected to be randomized will be premedicated for gout flare prevention. The regimen will begin at least 7 days prior to the first dosing of study drug and continue for as long as the patient is participating in the clinical study.

Patients not already taking colchicine will receive colchicine 1.2 mg as a single loading dose followed by 0.6 mg QD for the remainder of participation in the trial. If the patient cannot tolerate the loading dose level of 1.2 mg, then the patient will initiate and maintain colchicine at 0.6 mg per day. If the patient cannot tolerate the loading dose level of 0.6 mg, then the patient will initiate and maintain colchicine at 0.3 mg per day.

Patients with a documented medical reason that describes a contraindication to colchicine will receive ibuprofen 600 mg TID or an equivalent NSAID unless the patient has a contraindication to NSAID. At the discretion of the Investigator, a proton pump inhibitor may be prescribed with the NSAID as gastric prophylaxis. Patients with documented medical reasons that describe contraindications to both colchicine and NSAIDs will receive no premedication for gout flare.

Patients who began receiving a NSAID as gout flare prevention medication due to a contraindication to colchicine should continue to receive the NSAID during study participation.

As gout flares are expected to occur despite preventative premedication, incidents of gout flare are to be recorded as an AE and treated at the discretion of the Investigator to provide adequate patient care.

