12.2.1.2 Serious Adverse Event (SAE)

An SAE is any AE that occurs irrespective of study treatment assignment, if it satisfies any of these criteria:

- Results in death;
- Is life-threatening;
- Requires inpatient hospitalization \geq 24 hours or prolongs existing hospitalization;
- Results in persistent or significant disability or incapacity or substantial disruption of the ability to conduct normal life functions;
- Is a congenital anomaly or birth defect;
- Is an important medical event that, based upon appropriate medical judgment, may jeopardize the patient or patient may require medical or surgical intervention to prevent one of the outcomes listed above.

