12.2.2 Recording Adverse Events

Patients will be encouraged to spontaneously report any changes in health from the time of signing the ICF through completion of the study. Study staff will also inquire about any changes in the patient's health.

All AEs will be recorded in the source document and the CRF. It is the responsibility of the Investigator to review all documentation (e.g., hospital progress notes, laboratory, and diagnostics reports) for the presence of AEs and for a complete evaluation of known AEs.

At minimum for each AE, the Investigator will evaluate and report the event name/term/description, onset (date and time), resolution (date and time), event severity/intensity, relationship to study drug, action taken in regards to study drug, whether the event is an SAE, and whether or not it caused the patient to discontinue the study. The event time is only required while the patient is in the clinic.

During the Screening Phase (from time informed consent is signed to immediately before dosing) any clinically significant changes in the patient's health will be recorded in the patient's medical history and will not be considered as AEs.

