i) Exposure –adjusted event rate in treatment group A based on patients = Number of all patients with at least one event in treatment group A / Total sum of the treatment exposure time of all patients in treatment group A.

ii) Exposure –adjusted event rate in treatment group A based on events = Number of all events in treatment group A / Total sum of the treatment exposure time of all patients in treatment group A.

This document is confidential.

Listings of TEAEs and non-TEAEs will be provided. The treatment-emergent AEs for the double-blind treatment phase and for the double-blind extension phase will be flagged, respectively.

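### Events starting between consent and the first infusion, even serious ones caused by required procedures, are medical history only and bypass SAE reporting and every safety output

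*Protocol*

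**What the plan says.** Three protocol sections set the same starting point for adverse event collection.

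- 12.2.3.1 (reporting period): "The study period during which AEs must be reported is from the time the patient is dosed". For the time before that, it says "any clinically significant changes in the patient's health will be recorded in the patient's medical history and will not be considered as AEs".
- 12.2.2 (recording) repeats the rule and defines the window: "During the Screening Phase (from time informed consent is signed to immediately before dosing".
- 12.2.1.1 (AE definition) gives AEs and SAEs the same start: "and thus SAEs) will be collected from the time the patient is dosed (infusion is started".

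Section 12.2.1.2 makes every SAE a kind of AE: "An SAE is any AE that occurs irrespective of study treatment assignment, if it satisfies any of these criteria".

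The protocol requires several measures in the same window:

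- washout of at least 7 days for patients on ULT (7.1.1, 10.5);
- colchicine or an NSAID for flare prophylaxis, of which 10.6.1 says "The regimen will begin at least 7 days prior to the first dosing of study drug";
- prednisone, two fexofenadine doses and IV methylprednisolone before the first dose (10.6.2).

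On patients who never reach dosing, 8.3.1 says: "Any patient that is randomized but not dosed will be replaced and not included in the ITT population". The SAP's Safety Set (5.2) requires that some study medication was given.

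**The concern.** The trial imposes drug withdrawal and new medication on patients at a time when nothing that happens to them can be an AE. The rule makes no exception for serious events or for events that the investigator attributes to a required measure. Such an event would not go to the safety group within 24 hours, and the plan attaches no seriousness or causality assessment to it.

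Patient safety and the description of the whole regimen are at stake; the efficacy result is not. Section 12.2.3.1 asks investigators to report SAEs reasonably related to study drug even after a patient has left the study. There is no counterpart for a serious event during the washout or prophylaxis that the protocol itself requires.

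**Working it through.** The plan gives no figure to reproduce, so this is mainly a check of the text.

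**1. Can a pre-dose event be an SAE?** An SAE must first be an AE (12.2.1.2). A change in health between consent and the first infusion is not an AE (12.2.1.1, 12.2.2, 12.2.3.1). So it cannot be an SAE, and the 24-hour procedure in 12.2.3.2 is not triggered. I found no exception anywhere in the protocol or SAP.

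**2. Where does such an event appear?**

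- SAP 8.3: medical history is coded and listed for all randomized patients, with no summary.
- SAP 8.1: screen failures are listed with the reason for failure.
- SAP 8.4: the flare assessments at screening and baseline are summarised.
- SAP 10: safety analyses use the Safety Set or the Extension Phase Evaluable Set, and the AE tables and listings can show only what was recorded as an AE.

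The first three are baseline or disposition displays. None is a safety output, and the plan gives none of them seriousness or causality.

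**3. Can this affect a randomized patient?** Yes. Appendix A (footnote 15) allows randomization from Day -7 to Day 0. A patient randomized in that week who then cannot be dosed is replaced, and leaves both the ITT and the Safety Set.

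**4. Is the rule consistent for gout flares?** Not clearly. Section 10.6.1 tells sites to record flares as AEs and gives no start time, and 11.2.2 makes flare assessment part of AE collection. Under the screening rule, a flare during washout is medical history. The screening rule is the more specific text, but the two need to be reconciled. Such a flare can also prevent dosing under exclusion criterion 6.

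**5. How much of the first premedication is uncovered?** Only effects that begin before the infusion and do not worsen afterwards. From the timings in 10.6.2:

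- prednisone, 24 ± 12 h before dosing: 24 - 12 = 12 h to 24 + 12 = 36 h;
- methylprednisolone, 1 ± 0.5 h before dosing: 1 - 0.5 = 0.5 h to 1 + 0.5 = 1.5 h.

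Anything that starts or worsens after the infusion begins is a TEAE whatever its cause (protocol 12.2.1.1, SAP 10.3).

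**6. Size of the window.** Inputs: about 120 randomized patients (7.2) and a minimum lead-in of 7 days (7.1.1, 10.6.1).

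120 x 7 = 840 patient-days; 840 / 365.25 = about 2.3 patient-years.

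The window is longer where washout or prophylaxis starts earlier, as 7.1.1 permits, and patients who fail screening add to it. The documents give no event rate for this period, so no expected number of events can be calculated.

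**The case against.** The strongest defence is that this is a deliberate rule, not an oversight. It is stated three times without variation and fits the protocol's definition of an AE as an occurrence associated with use of the study drug. It changes no estimate and no confirmatory conclusion. Nor is the information lost: 12.2.2 encourages patients to report health changes from the signing of consent, and sites record them. All of this stands, which is why the point is an improvement rather than an error. It does not supply seriousness, causality or prompt reporting for a serious event caused by a required measure.

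A reader might also infer four stronger things that the documents do not support.

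- *That harms of the first premedication are not covered.* Only the short interval before infusion is uncovered; later onset or worsening is captured.
- *That the DSMB cannot see these events.* Its charter is a separate document (SAP 11) and was not available, so what it receives is unknown.
- *That the non-TEAE listing in SAP 10.3 would be empty.* The SAP says "Listings of TEAEs and non-TEAEs will be provided". Patients withdrawn from study drug continue visits to the end of Treatment Period 12, while the TEAE window closes 30 days after the last dose. Later off-drug AEs could fill the listing.
- *That the window should be sized at 45 days per patient.* That is the maximum length of screening (7.1), not exposure to the required measures. Washout applies only to patients on ULT, and some patients already take colchicine.

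**Conclusion.** The gap is real but narrow. An event with onset between consent and the start of the first infusion is neither an AE nor an SAE, however serious and whatever its cause. It triggers no 24-hour report and reaches no safety output. For scale, the window is at least 7 days per patient, or about 840 patient-days. That figure assumes 120 patients who each have the 7-day lead-in; a patient who is not on ULT and has contraindications to both colchicine and NSAIDs would not. The number of events missed is unknown.

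Events that start or worsen after the first infusion are captured, and the TEAE tables and the randomised comparison stand as planned. The conclusion assumes that the explicit screening rule governs where it meets 10.6.1, and that documents not supplied, such as the Study Operations Manual and CRF instructions, add no separate route for pre-dose serious events.

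**What to change.** Amend protocol 12.2.1.1, 12.2.2 and 12.2.3.1. From consent, or from the start of washout or prophylaxis, record the following as pre-treatment, non-treatment-emergent events:

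- all serious events;
- events attributed to a required procedure or medication;
- events that prevent the first dose.

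Report the serious ones within 24 hours by the existing route in 12.2.3.2. State in 10.6.1 how a flare during washout is to be recorded, so that it agrees with these sections.

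Add one listing to SAP 10.3 covering all randomized patients, including those not dosed, and screen failures. No split by arm is needed, because the pre-dose measures are the same in every arm. Leave the TEAE definition as it is. If screening has already closed, the listing could still be built from medical history entries dated between consent and first dose, where onset dates were recorded.

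The cost is protocol and CRF-guideline wording, a small number of extra SAE forms and one listing. The downside is slightly more site reporting before dosing.
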